### 10.4.3 Secondary endpoints

The secondary endpoint analyzable at the completion of recruitment is the reason(s) justifying the choice analyzed in 10.4.2. These will be tabulated by choice and compared, if appropriate, by chi square test or by ordinal logistic regression. Unplanned *post-hoc* subgroup analyses may be performed if requested by the Steering Committee.

The other secondary endpoints include the frequency of thromboembolic complications and the frequency of bleeding complications or death for any reason. These will be analyzed at the completion of each year of observation (full year of observation of the last subject entered into the long-term follow-up). The interim results will be used by the DMSB to decide on whether the observation has to continue or must be stopped. The final analysis will be adjusted for multiplicity using the nominal critical P value of 0.048.

Event rates will be reported at the available observations as proportion, stratified by sub-population, with the relevant confidence interval. Deviations from the expected rate of events will be analyzed by chi square and/or time to event by survival analysis. If appropriate, subgroups will be analyzed with the Cox survival model. Impact of putative predictors as indicated by the Steering Committee will be analyzed by logistic regression and/or Cox proportional-risk model.

Since clinically-relevant non-major bleeding may not be a reason for interrupting the follow-up, and minor bleedings are not a reason for interruption, it is possible that the number of bleeding events per subject can be submitted to analysis by Poisson regression.

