### 10.2 Sample size

The study anticipates recruiting approximately 3,200 subjects, based on considerations relevant to the primary endpoint.

The primary endpoint is the decision taken by the attending physician at the end of the maintenance anticoagulation initiated after the index event. Three options are possible: continue with extended anticoagulation (regardless of individual drug and dose), replace the anticoagulation with an antithrombotic, non-anticoagulant treatment, or stop any pharmacological prophylactic treatment.

In absence of other determinants, the null hypothesis is that the distribution of subjects by option is uniform. The analysis can therefore be performed with a goodness-of-fit test with 2 degrees of freedom. The alternative hypothesis is that at least one of the three choices is selected in a greater proportion than the other two. This analysis is performed once only at the end of recruitment.

With approximately 3,200 subjects, the study has 90% power to detect with 95% confidence a deviation from the uniform distribution, in case one of the options is selected in a proportion exceeding by 10% relative or more the proportion expected from the uniform distribution (i.e., in 36.3% or more of the subjects) [7].

Given that the factor “country” (synonymous of “healthcare system”) will be a likely cofactor in the analyses, the sample should be split across the participating countries in such a way to allow a reliable representativeness also for the smaller countries. The limit was considered not less than 100 subjects per country. The anticipated contribution by country was therefore estimated as:

Country	cases
China	approximately 200
Czechia	approximately 350
Mexico	approximately 300
Poland	approximately 900
Portugal	approximately 350
Romania	approximately 250
Russia	approximately 800
Slovakia	approximately 150
Tunisia	not less than 100

Since in this study the secondary endpoints are of clinical relevance as well, it is appropriate to estimate whether the indicated sample can yield reliable information also in relation to such endpoints.

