#### **10.4.4 Other endpoints**

Other monitored endpoints include the occurrence of hospitalization and the change of prophylactic therapy, including:

- institution – by the attending physician or other physician - of a therapy in subjects who stopped any prophylactic treatment at recruitment;
- change – by the attending physician or other physician - of the prophylactic treatment assigned at recruitment, and
- interruption – by the attending physician, other physician or by spontaneous subject's decision - of the prophylactic treatment assigned at recruitment.

Hospitalizations do not necessarily imply interruption of the follow-up, unless associated to a primary endpoint (thromboembolic event, bleeding, death) or result in the impossibility to continue an appropriate monitoring (e.g. need for anticoagulation). Consequently, hospitalizations can be analyzed by chi square across sub-populations as proportion of subjects with event or, in case of an appreciable number of events, by Poisson regression.

Any change in therapy, instead, implies interruption of the follow-up. Changes in therapy will be tabulated, stratified by sub-population, as absolute number and proportion and, if appropriate, analyzed by chi square and/or by logistic regression.

In addition, the reasons for study termination may be considered an endpoint. These will be tabulated by sub-population and compared, if appropriate, by chi square or ordinal logistic regression. If required by the Steering Committee, unplanned *post-hoc* subgroup analyses may also be performed.

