**Please specify whether compression therapy is prescribed:**

no:  0   yes:  1   specify mmHg recommended: |        | [text]

**Reasons for taking this decision  
(please tick all what applicable)**

No need of further treatment		0-no; 1-yes; default=no
Risk of thromboembolic recurrence		specify:  high-medium  low [HELP BOX FOR CRITERIA]
Risk of bleeding		specify:  high  medium  low [HELP BOX FOR CRITERIA]
Major bleeding event during treatment		
Difficulty to maintain the proper INR		
Consideration of patient's age		
Presence of Post Thrombotic Syndrome		
Presence of thrombophilia		specify: _____ [text]
Familiarity for venous thromboembolism		
Implantation of vena cava filter		
Presence of pulmonary hypertension		
Worsening of general conditions (not cancer)		
Worsening/onset of renal insufficiency		
Tendency to falls		
Presence of cancer		
Onset of contraindications		specify: _____ [text]
Decision by the patient's family doctor		
Choice of the patient		
Cost for the patient		
Positive D-dimer value		specify value:  _ _  D-DU  FEU 
Negative D-dimer value		specify value:  _ _  D-DU  FEU 
[if D-dimer value specified, one of the units MUST be specified]		
Patient involved in choosing the prescribed therapy		0-no; 1-yes; default=no
Patient's GP involved in choosing the prescribed therapy		0-no; 1-yes; default=no
Planned duration of this therapy:  not applicable [if decision=2, only possible choice]  not defined  to be evaluated  defined; specify:  _ _ _    months  years		

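### Ordinal logistic regression is named for the reasons for the decision and for study termination, but neither is an ordered outcome; the result depends on an arbitrary ordering

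*Combined protocol and SAP*

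**What the plan says.** Section 10.4.3 introduces the endpoint in these words: "The secondary endpoint analyzable at the completion of recruitment is the reason(s) justifying the choice analyzed in 10.4.2". On method it says: "These will be tabulated by choice and compared, if appropriate, by chi square test or by ordinal logistic regression". For the reasons for study termination, section 10.4.4 says: "These will be tabulated by sub-population and compared, if appropriate, by chi square or ordinal logistic regression". Both sentences recur in the statistical plan of the synopsis. None of these places says which variable is the ordinal outcome, how the chi-square table is laid out, or how multiple testing is handled.

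The data are defined in Appendix IV:

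- **Reasons for the decision.** The baseline form lists 21 reasons under the instruction "please tick all what applicable". Each is its own item, coded "0-no; 1-yes; default=no". There is no ranking and no field for a main reason. Two items carry a grade: risk of bleeding (three levels) and risk of recurrence (two levels).
- **Reasons for termination.** The end-of-study form lists nine reasons, each with its own box, and its check requires at least one to be marked. More than one is therefore possible.

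The decision itself has three options. Section 10.2 tests them against a uniform distribution by goodness of fit with 2 degrees of freedom, which is a nominal treatment.

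**The concern.** A proportional-odds model needs an outcome whose categories have a natural order. Three variables could serve as outcome here: the reason, the termination reason and the decision. The two lists have no order. Because several items can be ticked, they are not even a single variable per subject. The decision is never given an order and is analysed as nominal elsewhere.

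An analyst who follows the text must therefore invent an order, and the estimate then reflects that choice. The practical risk is a strong association reported as absent. This matters because the reasons are the first secondary endpoint listed in section 8.1.2, the synopsis also puts them in its statement of the primary objective, and section 7.1 makes the decisional process the research question.

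**Working it through.** **The plan's own figure.** No figure is given for the reasons. The nearest is the 90% power of the primary test in section 10.2, with 3,200 subjects and one option at 36.3%. Taking the other two at 31.85% each:

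- w² = 3 × [(0.363 − 0.3333)² + 2 × (0.3185 − 0.3333)²] = 0.00396, so w = 0.0629.
- Noncentrality = 3,200 × 0.00396 = 12.67.
- Power at 2 df and alpha 0.05 = 90.05%.

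The figure reproduces. It confirms that the decision is handled as nominal, and nothing below changes it.

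**Ordinal model with the decision as outcome.** The counts are illustrative; the documents give none. Options are a = extended anticoagulation, b = alternative antithrombotic, c = no drug prophylaxis.

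| | a | b | c |
|---|---|---|---|
| Reason ticked | 250 | 500 | 250 |
| Reason not ticked | 400 | 200 | 400 |

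- Nominal chi-square: expected counts are 325, 350, 325 in each row. X² = 4 × 75²/325 + 2 × 150²/350 = 69.2 + 128.6 = 197.8 on 2 df, p = 1e-43.
- Order a < b < c: the cumulative odds ratio at the first cut is (250/750)/(400/600) = 0.5, and at the second (750/250)/(600/400) = 2.0. They cancel, and the fitted odds ratio is 1.00, p = 1.0.
- Option b placed lowest: odds ratio 0.35, p about 1e-34.
- Option b placed highest: odds ratio 2.85, p about 1e-34.

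The values 0.35 and 2.85 are reciprocals and describe the same pattern from opposite ends. The serious failure is the 1.00.

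**Ordinal model with a reason as outcome.** This supposes that each subject were reduced to one of four unordered categories. Illustrative counts are 300/200/300/200 in one group and 200/300/200/300 in the other. The nominal chi-square is 8 × 50²/250 = 80 on 3 df, p = 3e-17. The proportional-odds ratio is 1.38 (p = 6e-5), 1.92 (p = 1e-15) or 1.00 (p = 1.0), depending only on the order assigned.

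**Chi-square.** Data were simulated with no true difference in reasons between decisions: 3,200 subjects, 20 or 21 yes/no reasons, about 1.7 to 6.3 ticks per subject, reasons independent or correlated, 500 to 1,000 runs per setting. Tick frequencies and correlations are assumptions.

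| Layout | Type I error at nominal 5% |
|---|---|
| One 2×3 table per reason, each subject counted once | 4.6% to 5.3% |
| One table pooling all ticks | 0.0% to 3.4% |

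**Multiplicity.** For 21 independent tests at 0.05, 1 − 0.95²¹ = 65.9% chance of at least one false positive (60% to 67% in the simulation). A Bonferroni level would be 0.05/21 = 0.0024.

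**Centre clustering.** The simulation above treated subjects as independent. Section 8.2.1 allows up to 40 subjects per centre, so 3,200 subjects could come from as few as 80 centres. Suppose decision and reason each vary between centres with the same intraclass correlation ρ and are otherwise unrelated. The variance inflation is then approximately D = 1 + 39ρ², and the true size of the 2-df test is exp(−5.99/(2D)).

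| ρ (assumed) | D | Size |
|---|---|---|
| 0.02 | 1.016 | 5.2% |
| 0.05 | 1.098 | 6.5% |
| 0.10 | 1.390 | 11.6% |
| 0.20 | 2.560 | 31.0% |

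The documents give no value for ρ.

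**The case against.** Four points can be made for the plan.

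1. **The comparison is conditional and exploratory.** It is made only if appropriate, section 10.1 calls all analyses descriptive and exploratory, and the committed output is the tabulation. This limits the consequence. It does not give the named model an ordered outcome.
2. **Something ordered does exist.** The bleeding-risk item is graded in three levels, and an ordinal model could be used for that grade. But it is a detail within one reason, whereas section 10.4.3 names the model for the reasons as a whole.
3. **The decision could be read as falling treatment intensity**, in the order in which the options are listed. The protocol never declares such a scale, and section 10.2 treats the options as exchangeable. That order is also the one under which the first illustration gives an odds ratio of 1.00, so it does not protect against missing a reason that favours the middle option.
4. **The chi-square is sound.** This stands. A reader might infer that both named methods fail because subjects are counted once per tick. The documents do not support that reading: section 10.4.3 prescribes no pooled table, and the form stores each reason as its own yes/no item, so one table per reason is the natural layout. Nor should a reader infer that pooling ticks would exaggerate significance; in every setting tried, the pooled test was conservative.

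**Conclusion.** The ordinal model is wrong as written for the reasons for the decision (section 10.4.3), for the reasons for termination (section 10.4.4) and for both in the synopsis. Its estimate depends on an arbitrary order and can turn a very strong association into an odds ratio of 1.00. The tables that show this are illustrative; they establish that the failure can happen, not how often it would in this study.

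The chi-square is acceptable when done reason by reason. What the text lacks there is a stated layout, a position on 21 tests and an allowance for centre. The calibration figures rest on assumed tick rates and correlations, and the clustering figures on assumed intraclass correlations.

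The correction should be made because a stated method is wrong and the change is cheap. It concerns a secondary, exploratory endpoint and, for termination, something that only may be treated as an endpoint. The primary test and sample size are untouched.

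**What to change.** Delete 'ordinal' in the synopsis, section 10.4.3 and section 10.4.4, and specify:

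- **Reasons for the decision.** For each reason, report the proportion ticking it by decision with a 95% confidence interval. Compare by a 2×3 chi-square that counts each subject once, by a binary logistic model for that reason with the decision as a categorical predictor, or by a multinomial logistic model of the three-level decision. Adjust the models for country and use centre-clustered standard errors.
- **Multiplicity.** State either that the 21 per-reason tests are exploratory and unadjusted, or which adjustment applies.
- **Reasons for termination.** Analyse each as yes/no by sub-population. Multinomial or cumulative-incidence methods are suitable only if a rule first assigns one primary reason per subject, since several can be marked.
- **Graded items.** If an ordinal model is wanted for the bleeding-risk grade, name that variable as its outcome.

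The cost is plan wording and slightly more analysis; no new data are needed. Reasons that almost determine the decision, such as the item stating that no further treatment is needed, may cause separation in the regression models and should be tabulated only.

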	
study, which is observational, it is not designed to confirm or reject predetermined hypotheses.
 
Populations
 
The analyses will be performed on the total sample monitored. Missing data will not be replaced.
 
Demographic, prognostic and descriptive variables
 
All variables will be summarized with the usual descriptive techniques: categorical variables as contingency table (absolute and relative frequency); continuous variables with sampling statistics: mean, standard deviation, median, minimum, maximum. Whenever appropriate the relevant 95% confidence interval will also be reported.
 
Primary endpoint
 
The primary endpoint will be analyzed at the completion of the recruitment. The proportion of choices made by the attending physician will be reported as proportion with confidence interval by level. The primary analysis will test by goodness-of-fit whether the choices were random or not. The impact of demographic and prognostic factors – including country – on the choice can be tested by chi square and/or logistic regression analysis.
 
Secondary endpoints
 
Frequency of thromboembolic complications and frequency of bleeding complications or death for any reason will be analyzed at the completion of each year of observation. The interim results will be used by the DMSB to decide on whether the observation has to continue or must be stopped. The final analysis will be adjusted for multiplicity using the nominal critical P value of 0.03.
 
Event rates will be reported at the available observations, stratified by sub-population, as proportion with the relevant confidence interval. Proportions will be compared if appropriate by chi square and/or as time to event by survival analysis.
 
Since clinically-relevant non-major bleeding may not be a reason for interrupting the follow-up, and minor bleeding are not a reason for interruption, it is possible that the number of bleeding events per subject can be submitted to analysis by Poisson regression.
 
The other secondary endpoint is the reason(s) justifying the choice analyzed as primary endpoint. These will be tabulated by choice and compared, if appropriate, by chi square test or by ordinal logistic regression. Unplanned post-hoc subgroup analyses may be performed if requested by the Steering Committee.
 
Other endpoints
 
Occurrence of hospitalization and changes of prophylactic therapy, including institution of a therapy in subjects who stopped any prophylactic treatment at recruitment; change of the prophylactic treatment assigned at recruitment, and interruption of the prophylactic treatment assigned at recruitment.
 
Hospitalizations will be analyzed as proportion of subjects with event, compared between sub-populations, if appropriate, by chi square or in case of an appreciable number of events, by Poisson regression.
 
Changes in therapy will be tabulated as absolute number and proportion stratified by sub-population and, if appropriate, analyzed by chi square and/or logistic regression. In addition, the reasons for study termination may be considered an endpoint. These will be tabulated by sub-population and compared, if appropriate, by chi square or ordinal logistic regression.
 
Safety observations
 
Adverse events will be handled by the attending physician according to the local procedures and, as in any observational study, will not be subject to statistical analysis. Only those events that resulted in the interruption of follow-up will be tabulated by sub-population and/or individual medication, without further statistical considerations.

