#### **4. End-of-study visit**

Each subject will have an end-of-study visit. This does not represent an independent visit, but a simple recording of the end of monitoring for the individual subject, and will coincide with:

- a. the last contact, usually at the center, at the end of the 2-year observation;
- b. the planned or unplanned follow-up visit at which any of the events terminating the follow-up have occurred, as indicated in the unplanned follow-up visit (thrombotic complication, major bleeding complication, substantial change in therapy, other event preventing continuation of the follow-up);
- c. the investigator is informed that the subject died;
- d. the subject ceased reporting to the center and started reporting to another hospital;
- e. the subject moved the residence to a place preventing continuation of the follow-up;
- f. the subject was lost to follow-up without additional information.

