## 10. Statistics

### 10.1 Statistical considerations

The statistical analyses will be descriptive and exploratory. Given the nature of the study, which is observational, it is not designed to confirm or reject predetermined hypotheses. The hypothesis indicated in the sample size calculation is to be considered supportive of the physicians' attitude towards methods of long-term prophylaxis, to be eventually confirmed by specifically designed motivational investigations.

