The secondary endpoints are the rate of thromboembolic complications and the combined rate of bleeding complications/death. To allow the DMSB (§ 11.3) to take appropriate decisions on the conduct of the study, these analyses will be performed at yearly intervals, i.e., when the last recruited subject has reached the end-of-year observation. There will therefore be 2 analyses (1 interim and one final), so that the final analysis will have to report as statistically relevant and deserving further investigations,  $P$ -values  $\leq 0.048$ .[8]

The interest of the study is to find whether any of the three constituted sub-populations – extended anticoagulation; long-term antithrombotic prophylaxis; no pharmacological prophylaxis (§ 8.1) – deviates from the expected risk, to an extent deserving investigation of the potential predictors of outcome.

From the literature [2, 3], the estimated annual risk of recurrence in the control group was approximately 5 events per 100 subject-years. The combined risk of bleeding or death was approximately 1 event per 100 subject-years.

Assuming that almost all recruited subjects will be monitored for at least one year, this survey has 80% power to detect with a two-tailed 95% confidence (after accounting for the interim analyses) a Cohen’s effect of the baseline decision taken on the follow-up outcomes, of 0.055 [9]. It can therefore identify as potentially relevant, deviations of at least one of the constituted sub-population from the anticipated recurrence rate of at least  $\pm 0.0123$  (3.77 or less, or 6.23 or more, events per 100 patients per year). Similarly, it has 80% power to detect with a two-tailed 95% confidence a deviation of at least one of the three constituted sub-populations from the anticipated bleeding/death rate of  $\pm 0.0055$  (0.45 or less, or 1.55 or more, events per 100 patients per year). [10]

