## 10.3 Populations

As usual in the observational studies, the analyses will be performed on the total sample monitored. Only subjects specifically indicated by the Steering Committee as major, irreconcilable deviation will be excluded from analysis (§ 11.1). Missing data will not be replaced. Subgroup analyses are not anticipated, however – given the exploratory nature of the study – unplanned subgroups analyses may be performed *post-hoc*, upon indications by the Steering Committee.

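### Event rates are to be reported and tested as crude proportions although the benchmarks are per 100 subject-years and follow-up closes early, with no denominator or censoring rule

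*Combined protocol and SAP*

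**What the plan says.** The benchmarks are in section 10.2. For recurrence, "the estimated annual risk of recurrence in the control group was approximately 5 events per 100 subject-years". For bleeding or death combined, the figure is 1 per 100 subject-years. The power statement there begins "Assuming that almost all recruited subjects will be monitored for at least one year". No closure rate is given for either year.

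The analysis is in section 10.4.3: "Event rates will be reported at the available observations as proportion, stratified by sub-population, with the relevant confidence interval". The next sentence reads: "Deviations from the expected rate of events will be analyzed by chi square and/or time to event by survival analysis". For comparisons between sub-populations the synopsis adds: "Proportions will be compared if appropriate by chi square and/or as time to event by survival analysis". Section 10.3 says that "the analyses will be performed on the total sample monitored" and that missing data are not replaced.

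Follow-up is planned for two years. Section 8.3.1 (end-of-study visit) closes it earlier for any of: "thrombotic complication, major bleeding complication, substantial change in therapy, other event preventing continuation of the follow-up". It also closes at death, transfer to another hospital, a move, or loss to follow-up. Section 10.4.4 treats any change of therapy as ending follow-up.

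**The concern.** A subject-year rate and a proportion of subjects are different quantities. They can be compared only if the rate is converted to a risk over a stated period and every subject is observed for that period, or if time at risk is used. The plan does neither. The annual rate is not converted to a 1-year or 2-year risk, and nothing says how a subject closed at, say, month 7 is counted. The two natural readings of the text give bias in opposite directions: downward if all enrolled subjects form the denominator, upward if only completers and subjects with events are counted.

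The grounds for closure also differ by sub-population. Starting a therapy closes untreated subjects; replacing or stopping one closes treated subjects. Unequal follow-up between the compared groups is therefore foreseeable.

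Section 7.1 makes the true event rate in each sub-population the secondary research question, and section 10.2 looks for deviation from the expected rate. A sub-population could appear to deviate only because of how long its subjects stayed on their assigned option. The same rates go to the data monitoring and safety board at the interim, and the final analysis flags P ≤ 0.048.

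**Working it through.** **The plan's own figure.** Section 10.2 states 80% power at a Cohen effect of 0.055 with 3,200 subjects. The noncentrality is 3,200 × 0.055² = 9.68. A 2-df chi-square then has power 0.802 at alpha 0.05 and 0.797 at 0.048, so the statement reproduces. The detectable deviations follow as 0.055 × √0.05 = 0.0123 and 0.055 × √0.01 = 0.0055. The sizing thus treats the annual rate as a one-year proportion, with all 3,200 subjects contributing.

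**Inputs.** From the documents: event rate λ = 0.05 (recurrence) or 0.01 (bleeding/death) per year, horizon t = 1 or 2 years, two-sided P = 0.048. Assumed: a constant closure hazard d per year, independent of risk, and 1,067 subjects per group (3,200 / 3).

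**Formulas.**
- All enrolled in the denominator: p = λ/(λ+d) × (1 − exp(−t(λ+d))).
- Completers plus subjects with events: p / (p + exp(−t(λ+d))).
- Mean person-time: (1 − exp(−t(λ+d)))/(λ+d). Events divided by person-time equal λ at every d.
- False flag: probability that a one-sample test rejects the benchmark risk when the true rate equals the benchmark. The 2-year benchmark is 1 − exp(−0.10) = 9.52%, the conversion most favourable to the plan.

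**Recurrence at 2 years, true rate exactly 5 per 100 subject-years.**

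| d per year | closed in year 1, 1 − exp(−d) | all enrolled | false flag | completers + events | false flag | events per 100 subject-years |
|---|---|---|---|---|---|---|
| 0 | 0% | 9.5% | 4.8% | 9.5% | 4.8% | 5.0 |
| 0.05 | 4.9% | 9.1% | 7.2% | 10.0% | 7.9% | 5.0 |
| 0.1 | 9.5% | 8.6% | 14.9% | 10.4% | 16.2% | 5.0 |
| 0.2 | 18% | 7.9% | 43.8% | 11.5% | 44.0% | 5.0 |
| 0.4 | 33% | 6.6% | 93.4% | 14.0% | 88.5% | 5.0 |

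**Variations, all enrolled in the denominator.**
- At 1 year against 1 − exp(−0.05): 4.9% at d = 0.05 and 5.7% at d = 0.1.
- Group size at d = 0.1, 2 years: 9.9% with 600 subjects, 25.2% with 2,000.
- If the annual rate is simply doubled to a 10% benchmark, 7.4% are flagged with no closure at all.
- Bleeding/death at 2 years: 4.8, 5.8, 10.2 and 26.1% at d = 0.05, 0.1, 0.2 and 0.4.
- Two groups with the same true recurrence rate differ falsely at 2 years in 6.1% (d = 0.05 vs 0.10), 9.6% (0.1 vs 0.2) and 42% (0.1 vs 0.4).
- Closure of about 22% per year brings the crude 2-year proportion, divided by two, to 3.77 per 100 per year. That is the plan's own lower detection limit, reached with no true deviation.

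**The alternative under the same conditions.** In 10,000 simulated trials per setting, the exact Poisson test on person-time rejected in 3.8% to 4.4% and the censored log-rank test in 4.6% to 5.0%.

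**If closure is related to risk.** Take half the subjects at 3 and half at 7 events per 100 subject-years. Without closure the person-time rate is 4.96 and the 2-year proportion 9.44%. Closure hazards of 0.05 and 0.1, assigned either way round, give 4.91 or 5.01. Hazards of 0.1 and 0.4 give 4.70 or 5.23, about 5% off. The all-enrolled proportion in that last case is 7.18% or 7.95%, which is 24% or 16% too low.

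**The case against.** The case for leaving the text alone has five parts.

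- *Survival analysis is already named.* The closing events are listed and dated, and a survival analysis would ordinarily censor there. This is true and makes the fix easy. But the method is optional, its censoring rule is unwritten, and nothing says what happens when an event for one endpoint closes follow-up for the other.
- *The chi-square could compare observed with expected events based on person-time.* The text does not support this reading: section 10.4.3 and the synopsis speak of proportions, and the sizing treats the rate as a proportion over all subjects.
- *The effect is small under the plan's own assumption.* This stands for year 1. Follow-up runs for two years, however, and nothing bounds closure in year 2. Hazards of 0.2 and 0.4 go beyond the one-year assumption and show only how the bias grows. The completer denominator and the 10% benchmark are possible readings; the plan prescribes neither.
- *The study is exploratory.* Section 10.1 says "it is not designed to confirm or reject predetermined hypotheses", and the groups are chosen by physicians, so confounding may outweigh modest closure bias. This limits the stakes, but an estimated rate can be biased whether or not a hypothesis is tested.
- *The critical P value is itself unsettled.* The synopsis gives 0.03 where section 10.4.3 gives 0.048. At 0.03 the 2-year false-flag rates at hazards 0.05 and 0.1 are 4.7% and 10.7%. The size changes; the bias remains.

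**Conclusion.** The concern holds and should be fixed. A route that the plan permits gives event rates on a different scale from their benchmarks, and the unstated denominator decides the direction of the bias. For recurrence at 2 years, with all enrolled subjects in the denominator, the false-flag rate is 7.2% at a closure hazard of 0.05 per year and 14.9% at 0.1, against a nominal 4.8%. It rises steeply with more closure. It is negligible at 1 year with little closure, and smaller for bleeding/death.

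These figures rest on assumed closure hazards, equal thirds, constant hazards and closure unrelated to risk. The primary endpoint and the stated power are not affected.

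**What to change.** In section 10.4.3 and the matching synopsis text:

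1. Report first events per 100 subject-years at risk, by sub-population, with exact Poisson confidence intervals, and compare these with 5 and 1 per 100 subject-years.
2. Replace the open choice of test with time-to-event analysis from the baseline visit, censored at therapy change, other closing event, loss to follow-up or month 24. For the thromboembolic endpoint, also end time at risk at death and at a major bleed that closes follow-up. For bleeding/death, end it at a thromboembolic event that closes follow-up. If a cumulative incidence of thromboembolic events is shown, treat death as a competing event. Crude proportions may be tabulated but not tested.
3. State that censoring at therapy change assumes the change is unrelated to risk, and read the results beside the termination reasons already tabulated under section 10.4.4. State that comparisons between physician-chosen groups are descriptive unless adjusted for baseline prognostic factors.

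Minor items: give a rule for closing dates recorded without a day, and record a date for clinically relevant non-major bleeds or use the contact date. Also reconcile the passages that set the censoring time. The synopsis, section 8.3.1 and section 10.4.4 differ on whether a switch within the same class closes follow-up. Section 8.3.1 and the follow-up form differ on whether a major bleed always does.

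Items 1 to 3 are wording on data already planned, because the end-of-study form dates the closing reasons; no visits or subjects are added. The minor items need at most one e-CRF date field. If closure is related to risk, person-time rates keep some bias, but less than the proportion has.
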